## **8. STUDY POPULATION PARAMETERS**

Listings will be done for the ITT population and summaries for the safety population. Some or all summaries may also be done for other analysis populations defined in [Section 6](#). Study population parameters to be listed and summarized are described below.

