### 3 INVESTIGATIONAL PLAN

#### 3.1 Overall Study Design and Plan

Male subjects with cardiomyopathy secondary to DMD meeting all inclusion and no exclusion criteria will be randomized. All subjects will be at least 12 years of age. They will be randomized in a 1:1 manner to either intracoronary infusion of CAP-1002 in three coronary arteries supplying the three major cardiac territories of the left ventricle of the heart (anterior, lateral, inferior/posterior) or usual care. In the active treatment arm, all three major cardiac territories will be treated (infused) during a single procedure in an open-label fashion.

Approximately 24, and not more than 30, subjects will be randomized into the study, in two sequential enrollment groups. Safety data from Group 1 will undergo a Data Safety Monitoring Board (DSMB) review prior to initiation of enrollment for Group 2.

The first 6-8 randomized subjects will comprise Group 1, and will include a minimum of 3 subjects completing intracoronary infusion with CAP-1002. The DSMB will conduct a review of interim safety data through 72 hours post-Day 0 for at least 3 infused subjects and for at least 6 subjects overall.

Enrollment of Group 2 will begin per DSMB recommendations following their review of the 72 hour safety data from Group 1. Group 2 will include approximately 18 subjects. Screening and randomization will continue until a total of 12 subjects are infused with CAP-1002 or 30 subjects are randomized into the study, whichever comes first.

CCI

A large rectangular area of the page is completely blacked out, indicating redacted content. The text 'CCI' is printed in red at the top left corner of this redacted area.

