## 6. ANALYSIS POPULATIONS

The following analysis populations are defined for the trial:

**Safety Population:** Subjects randomized to CAP-1002 treatment who received the IP on Day 0, and all subjects in the usual care treatment group who remain on study as of the reference time point. Subjects will be summarized and analyzed per treatment actually received, regardless of their randomization assignment.

Intent to Treat (ITT) Population: All subjects randomized. Subjects will be summarized and analyzed per their randomization assignment, regardless of the treatment (CAP-1002 or usual care) actually received.

Modified ITT (mITT) Population for Efficacy Parameter X: Subjects in the safety population who have at least one post-baseline observation for Parameter X. Subjects will be summarized and analyzed per their randomization assignment, regardless of the treatment actually received.

Per Protocol Population: Subjects with no major protocol violations. The list of subjects with major protocol violations will be compiled prior to database lock.

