### **8.6 IP Administration**

Details of IP administration will be listed. Successful completion of IP administration, reason for non-completion, combination of coronary territories infused, total dosage, and final TIMI flow score per artery infused will be summarized.

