### **8.8 Subject Disposition**

A listing of subject disposition will include dates of randomization and IP administration (or attempt) or reference date, whether or not the subject completed the Month 12 visit, subject-level EOS date, reason for study discontinuation (if applicable), and whether or not the subject consented to annual LTFUP. Frequencies and percentages of subjects who discontinued and reasons for discontinuation as well as duration of follow-up will be summarized. Duration of follow-up will be calculated as:

$$\text{duration} = \text{date of last known status} - \text{randomization date} + 1$$

where date of last known status is the maximum date among AE start and end dates, concomitant medication start and stop dates, visit dates (including unscheduled visits), and EOS date.

The summary table will include a p-value for treatment group comparison of discontinuation for any reason and, if appropriate, for duration of follow-up based on a log rank test.

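### The committed summaries of IP administration, visits and disposition use the safety population, so they omit randomized subjects never infused or gone before the reference time point

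*SAP*

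**What the plan says.** The opening of SAP Section 8 sets the populations for everything in that section: "Listings will be done for the ITT population and summaries for the safety population". It then adds, pointing to Section 6, "Some or all summaries may also be done for other analysis populations defined in". That sentence allows other versions and commits to none.

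The relevant definitions in SAP Section 6 are:

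- Safety population, CAP-1002 arm: "Subjects randomized to CAP-1002 treatment who received the IP on Day 0".
- Safety population, usual care arm: "all subjects in the usual care treatment group who remain on study as of the reference time point". SAP 2.3.1 puts that point at 9:00 a.m. on the seventh day after randomization.
- "Intent to Treat (ITT) Population: All subjects randomized".

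Three subsections name no population of their own, so the default applies to them:

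- SAP 8.6 summarizes "Successful completion of IP administration, reason for non-completion, combination of coronary territories infused, total dosage" and final TIMI flow.
- SAP 8.7 summarizes how many subjects completed each visit.
- SAP 8.8 summarizes discontinuations, reasons and duration of follow-up. It adds: "The summary table will include a p-value for treatment group comparison of discontinuation for any reason". Duration is counted from the randomization date.

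Protocol 3.1 leaves room for subjects who are randomized but not infused: "Screening and randomization will continue until a total of 12 subjects are infused with CAP-1002 or 30 subjects are randomized into the study". The earlier of these two limits applies.

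**The concern.** A completion table is meant to show how many of the subjects assigned to a procedure had it, and why the others did not. A disposition table is meant to account for everyone randomized. Here the denominator is fixed after the first losses can already have happened.

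In 8.6, non-completion can only mean a partial infusion. A subject in whom the procedure was never attempted, or was attempted with no cells given, is outside the table. In 8.8, a subject who leaves between randomization and Day 0 is outside the table, although follow-up in the same subsection starts at randomization. The two arms are also selected differently: one on having been infused, the other on still being on study after 7 days. The discontinuation p-value therefore compares two selected sets and not the groups formed by randomization.

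With about 12 subjects per arm (SAP Section 4), one omitted subject moves a percentage by several points.

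**Working it through.** The plan states no figure to reproduce. The check is which subjects can enter each table, followed by an illustration of the effect on the percentages.

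**Who can enter the committed tables**

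| Subject | 8.6 to 8.8 summaries (safety population) | ITT listings |
|---|---|---|
| CAP-1002, full infusion | yes | yes |
| CAP-1002, partial infusion | yes | yes |
| CAP-1002, attempted, no cells given | no | yes |
| CAP-1002, never attempted | no | yes |
| Usual care, on study at the reference time point | yes | yes |
| Usual care, left earlier | no | yes |

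**Inputs for the illustration**

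- 12 infused and at most 30 randomized: Protocol 3.1.
- 1:1 allocation: Protocol 5.3. At 30 randomized this is about 30/2 = 15 per arm.
- Number never infused, k: not given in the documents. Assumed range 0 to 3, so that 12 + k runs from 12 to 15.

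**Completion**

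Safety denominator: completed / 12. ITT denominator: completed / (12 + k).

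| k | Safety, all 12 complete | ITT, all 12 complete | Safety, one partial | ITT, one partial |
|---|---|---|---|---|
| 0 | 12/12 = 100% | 12/12 = 100% | 11/12 = 91.7% | 11/12 = 91.7% |
| 1 | 12/12 = 100% | 12/13 = 92.3% | 11/12 = 91.7% | 11/13 = 84.6% |
| 2 | 12/12 = 100% | 12/14 = 85.7% | 11/12 = 91.7% | 11/14 = 78.6% |
| 3 | 12/12 = 100% | 12/15 = 80.0% | 11/12 = 91.7% | 11/15 = 73.3% |

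The safety column does not change with k. Non-infusion cannot lower the reported completion rate; only a partial infusion can.

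**Retention**

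Suppose the k never-infused subjects leave the study and one infused subject leaves later. The CAP-1002 retention figures are then the same fractions as in the one-partial columns: 91.7% on the safety denominator for every k, against 91.7%, 84.6%, 78.6% and 73.3% on ITT.

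**Discontinuation comparison**

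Take k = 3, all three leaving, plus one later dropout in each arm and no early loss in usual care.

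- Safety population: 1/12 (8.3%) v 1/15 (6.7%).
- All randomized: (3 + 1)/15 = 4/15 (26.7%) v 1/15 (6.7%).

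Both tables have cells below 5, so the rule in SAP 7.3 calls for Fisher's exact test. The two-sided p-values are 1.00 and 0.33. The rates differ clearly, but the test is non-significant either way.

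**The case against.** The strongest reply is that nothing is lost. SAP Section 8 commits listings for all randomized subjects. The 8.8 listing gives the date of infusion or attempt, the end-of-study date and the reason for discontinuation. SAP 7.2 appends all tables, figures and listings to the study report, and 30 subjects at most can be read line by line. The 8.1 population table gives the ITT and safety counts, from which the share infused can be worked out if it is shown by arm. ITT summaries are also permitted. All of this stands, so a reader who infers that never-infused subjects vanish from the report would be wrong. But listings give no rates and no comparison between arms, the 8.1 counts give no reasons, and an optional summary can be decided on after open-label results are known.

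Other stronger readings also lack support:

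- *That the primary tolerability assessment is biased.* Protocol 9.5.1 bases it on TIMI flow, cardiac events, adverse events, laboratory values, vital signs, examination and ECG. Completion and attrition are not listed there.
- *That the baseline table (8.3) is wrong too.* The main safety analysis uses the safety population, and the mITT population in the SAP is drawn from it. A baseline table on the safety population describes closely the subjects analysed, and no harm from it can be shown.
- *That dropout in reaction to open-label allocation is likely before Day 0.* The documents give no data on this. The cap of 30 randomized allows for non-infusion; it does not predict a rate.
- *That reported completion is forced to 100%.* Partial infusions remain in the table.

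**Conclusion.** The point holds as a reporting defect in the committed summary tables of SAP 8.6, 8.7 and 8.8. It is a stated rule that gives the wrong denominator, not a missing detail. Its size depends on how many randomized subjects are not infused or leave before the reference time point, and the documents do not give that number. The overstatement is zero if there are none. For an assumed 1 to 3 never infused beside 12 infused, all complete, it is 100 - 92.3 = 7.7 to 100 - 80.0 = 20 percentage points for completion. For retention, with one later dropout and all never-infused subjects leaving, it is 91.7 - 84.6 = 7.1 to 91.7 - 73.3 = 18.4 points. A reader might infer that a significance result would change; the worked case does not show that. What is affected is the reported rates and reasons, and the standing of the discontinuation test as a comparison of randomized groups. It should be corrected, but it does not threaten the trial's main safety analysis.

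**What to change.** Amend the opening of SAP Section 8 so that the summaries in 8.6, 8.7 and 8.8, including the discontinuation p-value and the duration of follow-up, use the ITT population by randomized arm. In 8.6, make all subjects randomized to CAP-1002 the denominator, with separate rows for not attempted, attempted with no cells given, partial and complete, and reasons for each outcome short of complete. Keep the safety-population versions as secondary tables. The baseline table in 8.3 may stay on the safety population, with an ITT version optional.

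The cost is a revised sentence and a different population flag in three tables. The data are already in the ITT listings. For 8.7, SAP 7.6 ties Day 0 to the planned infusion day, so visit windows can be assigned to a never-infused subject if a planned date was recorded. The only downside is that completion and discontinuation figures may look slightly less favourable.

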### **8.1 Analysis Populations**

The analysis populations defined in [Section 6](#) will be described in terms of the identification of subjects in each population and the frequency distribution of each population.

### **8.2 Eligibility and Informed Consent**

Eligibility and informed consent parameters will be listed and will include protocol version, date of informed consent, and inclusion and/or exclusion criteria that were not met. Satisfaction of inclusion/exclusion criteria will be summarized.

### **8.3 Baseline Characteristics**

Demographic and other baseline characteristics will be listed and summarized and will include study site, age, race, ethnicity, Latin or Hispanic origin, DMD genetic analysis, and frequency of wheelchair use. Age will be computed in SAS as follows:

$$\text{AGE} = \text{floor}((\text{intck}(\text{'MONTH'}, \text{bdt}, \text{rdt}) - (\text{day}(\text{rdt}) < \text{day}(\text{bdt}))) / 12)$$

where bdt = birth date in SAS date format and rdt = randomization date in SAS date format.

Differences in baseline parameters by treatment group will be analyzed and p-values will be included in the summary table.

### **8.4 Medical History**

General medical history and cardiac history will be listed and summarized separately. The general medical history summary will include frequency of subjects with each condition. For cardiac history, the number of subjects with each condition and other condition-specific details will be summarized. Differences in medical and cardiac history by treatment group will be analyzed and p-values (for frequencies only) will be included in the summary table.

### **8.5 Serology and Coagulation**

Serology laboratory evaluations will include human immunodeficiency virus (HIV), hepatitis B surface antigen (HBsAg), and hepatitis C virus (HCV) and will be done at screening.

Coagulation laboratory evaluations will be done pre-infusion (CAP-1002 subjects only).

Serology and coagulation parameters will be listed and summarized.

### **8.6 IP Administration**

Details of IP administration will be listed. Successful completion of IP administration, reason for non-completion, combination of coronary territories infused, total dosage, and final TIMI flow score per artery infused will be summarized.

### **8.7 Subject Study Progress**

A listing of subject study progress will show dates of screening, informed consent, randomization, IP administration, study visits, and EOS. Number of subjects who completed each visit will be summarized.

### **8.8 Subject Disposition**

A listing of subject disposition will include dates of randomization and IP administration (or attempt) or reference date, whether or not the subject completed the Month 12 visit, subject-level EOS date, reason for study discontinuation (if applicable), and whether or not the subject consented to annual LTFUP. Frequencies and percentages of subjects who discontinued and reasons for discontinuation as well as duration of follow-up will be summarized. Duration of follow-up will be calculated as:

$$\text{duration} = \text{date of last known status} - \text{randomization date} + 1$$

where date of last known status is the maximum date among AE start and end dates, concomitant medication start and stop dates, visit dates (including unscheduled visits), and EOS date.

The summary table will include a p-value for treatment group comparison of discontinuation for any reason and, if appropriate, for duration of follow-up based on a log rank test.

## 9. SAFETY ANALYSIS

Listings, summaries, and analyses of safety parameters will be done for the safety population. Some or all summaries may also be done for other analysis populations defined in [Section 6](#). Safety parameters are described below.

### 9.1 Adjudicated Clinical Events

Clinical events, described in [Section 2.3.1](#), will be adjudicated by an independent Clinical Events Committee (CEC) (see [Section 12](#)). Each event will be summarized as frequency and percentage of subjects who experienced the event. In addition, a composite event will be defined as new TIMI flow 0-2 or TMPG 0-2 (CAP-1002 subjects only), sudden death, or MACE during or following IP administration or reference time point. For the composite and its components, summaries will include exact 90% confidence intervals (CIs) for both treatment groups. For peri-procedural events other than TIMI flow 0-2 or TMPG 0-2, summaries will include a 90% CI for the difference in proportions between treatment groups, and the one-sided p-value from an exact binomial test of the difference between treatment groups. For all other clinical events, assessed over the length of the trial, event rates per 100 subject-years will be calculated and, if applicable, treatment groups will be compared using negative binomial regression with an offset for days of follow-up (log transformed). If the dispersion parameter is not significantly different from zero, Poisson regression will be used instead.

For the analysis of development of increased HLA antibodies to HLA antigens specific to the CAP-1002 donor, incidence of increased HLA antibody levels specific to the donor will be summarized and analyzed; for usual care subjects, a random donor will be selected from those that were matched to the subject during screening. Elevated levels of donor specific antibodies will also be summarized and analyzed by time point for all nominal time points at which samples were collected for DSA testing. Analyses will be performed using both 1000 and 5000 MFI as the threshold for defining increased HLA antibodies.

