## 6.7 Continuous Cardiac Rhythm Monitoring

The sponsor will provide a wearable, wireless device for continuous cardiac rhythm monitoring. Subjects will wear a monitoring device for defined short-term intervals, starting at screening, on Day 1, and at the Week 6, Month 6, and Month 12 study visits. Table 3 details the continuous monitoring duration required at each study visit. The monitoring is

used to detect and record arrhythmias. All changes and any associated clinical significance will be evaluated and documented on the case report form.

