**Table 3. Per-Visit Minimum Continuous Cardiac Monitoring Durations**

Study Visit	Minimum Continuous Monitoring Duration
Screening	24 hours
Day 1	72 hours
Week 6	72 hours
Month 6	7 days
Month 12	72 hours

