**Day 1 for ALL SUBJECTS:**

- Initiate 72-hour continuous cardiac rhythm monitoring using sponsor-supplied monitor system (indicated for home use)
- No study visit is required for Day 1, as subjects will receive prior instruction on use of the monitoring system

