### **2.3 Study Assessments**

#### **2.3.1 Safety Assessments**

Safety will be assessed at 6 and 12 months post infusion or reference date unless otherwise noted. For usual care subjects, the reference time point will be randomization date + 7 days at 9:00 a.m. (subject's local time).

1) Adjudicated clinical events:

- a) The following events occurring during or post infusion or reference time point:

- For subjects who receive CAP-1002 only, new TIMI flow 0-2 or TIMI myocardial perfusion grade (TMPG) 0-2, noted immediately following intracoronary infusion of investigational product (IP) and persisting > 3 min after IP infusion, despite intracoronary vasodilator administration.
- Within 72 hours of intracoronary infusion or reference time point, sudden unexpected death defined as occurring within 1 hour of symptom onset, or unwitnessed death in a person previously observed to be well within the preceding 24 hours without an identified cause.
- Major adverse cardiac events (MACE) within 72 hours of intracoronary infusion or reference time point, including death, non-fatal myocardial infarction and hospitalization for cardiovascular event (including heart failure hospitalizations). Evidence of myocardial injury will be assessed by a rule out myocardial infarction (MI) cardiac enzyme protocol following IP administration. Among subjects who receive CAP-1002, troponin and creatine phosphokinase MB isoenzyme (CK-MB) will be obtained every 8 hours for 20-24 hours after IP infusion.

b) Sudden unexpected death defined as occurring within one hour of symptom onset, or unwitnessed death in a person previously observed to be well within the preceding 24 hours without an identified cause.

c) MACE, including death, non-fatal myocardial infarction, hospitalization for cardiovascular event (including heart failure hospitalizations), emergency room treatment for heart failure, left ventricular assist device or heart transplant.

d) Any hospitalization due to a cardiovascular cause.

e) Any inter-current cardiovascular illness which prolongs hospitalization.

f) Development of, or an increase in the frequency of, ventricular tachycardia (VT) with duration of 30 seconds or longer ascertained by protocol mandated continuous cardiac monitoring via Holter Monitor or ZIO® Patch.

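### SAP 9.1 puts sustained VT on a denominator and offset of total follow-up time, although item 1f can be ascertained only during scheduled monitoring, a minimum of 16 of about 360 days

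*SAP*

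**What the plan says.** SAP 2.3.1 lists new or more frequent VT of at least 30 seconds as adjudicated clinical event 1f, "ascertained by protocol mandated continuous cardiac monitoring via Holter Monitor or ZIO® Patch".

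For clinical events outside the peri-procedural period, SAP 9.1 states: "For all other clinical events, assessed over the length of the trial, event rates per 100 subject-years will be calculated". Where a comparison applies, the arms are compared by "negative binomial regression with an offset for days of follow-up (log transformed"), with Poisson regression as the fallback. Only the HLA antibody event gets a separate method; VT gets no exception. The words about applicability qualify the comparison, not the rate. The same section also reports each event as the frequency and percentage of subjects affected.

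SAP 9.1 does not define days of follow-up. The nearest definition is in SAP 8.8 ("Duration of follow-up will be calculated as"), which counts from randomization to last known status.

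Protocol 6.7 makes the monitoring intermittent: "Subjects will wear a monitoring device for defined short-term intervals". Protocol Table 3, under the column "Minimum Continuous Monitoring Duration", gives 72 hours at Day 1, 72 hours at Week 6, 7 days at Month 6 and 72 hours at Month 12, after a 24-hour recording at screening. SAP 9.7 lists the start and stop date and time of every recording but does not use them as a denominator.

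**The concern.** A rate per subject-year is meaningful when an event could have been recorded at any time in that year. MACE and cardiovascular hospitalization meet that condition. Item 1f does not: on the days without a device, an episode cannot be ascertained in the way the endpoint requires. Those days still enter the denominator as if they had been observed and were event-free.

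Two things follow. The absolute VT rate comes out too low and stands beside MACE rates in the same units, which invites a false comparison. And the offset adjusts for the wrong exposure whenever recorded time is not proportional to follow-up.

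This matters because safety is the primary objective, the product is infused into the coronary arteries, and SAP 9.7 does not name VT among the rhythm measures that it summarises. SAP 9.1 is therefore the only place with a specified analysis of the VT endpoint.

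**Working it through.** The documents give no VT rate or total monitored time, so there is no figure of the plan's own to reproduce.

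**Inputs.** Recording minimums after Day 0: Protocol Table 3. Length of follow-up: 360 ± 30 days, Protocol 7.8. About 12 subjects per arm: SAP 4.

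**Monitored share of follow-up**

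- Monitored days = 3 + 3 + 7 + 3 = 16.
- Share = 16/360 = 4.4%.
- Understatement factor = follow-up days / monitored days = 360/16 = 22.5. This assumes that episodes are counted, that their rate is constant, and that wear equals the minimum.

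**How the factor moves**

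| Variation | Calculation | Factor |
|---|---|---|
| Earliest Month 12 visit | 330/16 | 20.6 |
| Latest Month 12 visit | 390/16 | 24.4 |
| Follow-up per SAP 8.8, Day 0 seven days after randomization | (360 + 7 + 1)/16 | 23.0 |
| One day of in-hospital telemetry counted (CAP-1002 arm only) | 360/17 | 21.2 |
| SAP Appendix A, four 24-hour recordings after Day 0 | 360/4 | 90 |

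If each subject is counted once, the factor is 22.5 × [−ln(1 − p)/p], where p is the proportion affected. For 1 of 12 subjects it is 23.5; for 6 of 12 it is 31.2.

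**Example: one episode among 12 completers**

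- On follow-up time: 100 × 1/(12 × 360/365.25) = 8.5 per 100 subject-years.
- On monitored time: 100 × 1/(12 × 16/365.25) = 190 per 100 monitored subject-years, or 100 × 1/(12 × 16) = 0.52 per 100 monitored days.

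**Does the offset track exposure?** For an early leaver, take the share of a completer's monitored days divided by the share of a completer's follow-up. The offset is right only if this equals 1. Protocol Appendix 1 marks rhythm monitoring at Early Termination. Table 3 gives it no duration, but Protocol 7.11 asks staff to attempt the Month 12 testing, which Protocol 7.8 sets at 72 hours. Both cases are shown.

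| Leaves at | No Early Termination recording | 72-hour recording obtained |
|---|---|---|
| Day 170 | (6/16)/(170/360) = 0.79 | (9/16)/(170/360) = 1.19 |
| Day 200 | (13/16)/(200/360) = 1.46 | (16/16)/(200/360) = 1.80 |

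A value below 1 means that the offset credits the subject with too much monitored time; above 1, too little. Monitored time accrues in steps, so even the direction depends on when the subject leaves and whether the last recording is obtained.

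**Incomplete wear.** If one arm recorded 12 of 16 days and the other all 16, a true rate ratio of 1 would appear as 12/16 = 0.75. With complete follow-up and equal wear, the factor is common to both arms and cancels from the ratio.

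**The case against.** The strongest reply is that readers and the DSMB do not depend on this rate. SAP 9.1 already reports n (%) of subjects with each event, and with about 12 per arm that is the figure most people will read. SAP 14 also gives the DSMB the continuous monitoring data. This stands. A reader might infer that the plan hides VT events from the DSMB; the documents do not support that.

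The 22.5 is also conditional. It needs a constant episode rate. The first recording starts on Day 1, so if episodes cluster after the infusion, scaling the monitored rate up to a year would overstate the annual rate. Item 1f is worded as a change from baseline, and the SAP does not say whether episodes or subjects are counted. Table 3 gives minimums, so longer wear lowers the factor and missed wear raises it. All of this stands. It limits how precisely the error can be stated, but it does not make unmonitored days observed.

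On the comparison, both arms follow the same device schedule: under its Day 1 heading for all subjects, Protocol 7.2 has "Initiate 72-hour continuous cardiac rhythm monitoring using sponsor-supplied monitor system". No dropout or wear figures are given, SAP 10 expects very few missing observations, and the model is run only if applicable. A reader might infer that the rate ratio is biased; nothing in the documents shows that it will be. What remains is that the offset offers no protection if follow-up or wear does differ.

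Finally, a symptomatic episode between recordings could surface as an adverse event or a cardiovascular hospitalization. Item 1f as worded would still not count it.

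**Conclusion.** The point holds for the absolute VT rate and for the choice of offset. Followed as written, SAP 9.1 produces a VT rate on a denominator of which about 4.4% is scheduled as monitored under Protocol Table 3. The understatement is about 22.5-fold, given counted episodes, a constant rate, minimum wear and 360 days of follow-up. It is 20.6 to 24.4 across the Month 12 window and 90 under SAP Appendix A. It should not be read as an unconditional statement that the rate is 22 times too low.

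The n (%) of subjects is not affected by this denominator, and the between-arm rate ratio is unbiased when follow-up and wear are equal. For early leavers, the exposure error relative to a completer ranges from 0.79 to 1.80 in the cases worked.

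This should be changed before the analysis. It does not threaten the trial's safety assessment as a whole.

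**What to change.** In SAP 9.1:

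- Exempt item 1f from the rule on subject-years of follow-up.
- Keep the n (%) of subjects with VT.
- State whether episodes or subjects are counted.
- Give any VT rate per 100 monitored days.
- In any between-arm model for VT, use as offset the log of recorded monitor days after Day 0, derived from the start and stop times in SAP 9.7.
- Tabulate recorded days by arm and visit, including Early Termination recordings.

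Separately, the Holter/ZIO wording in SAP 2.3.1 item 1f and the 24-hour recordings in SAP Appendix A must be reconciled with Protocol Table 3, because the size of the monitored denominator depends on which schedule applies.

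The cost is SAP wording and one derived variable. SAP 9.7 names start and stop times but not analysable time, so a denominator restricted to analysable recording would need that item from the device data. The reported VT rate will look less favourable. No study procedure changes.
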